5.1. Overall Design

This is a Phase 1, parallel, placebo-controlled, fixed-sequence study with open-label administration of topiramate and investigator- and subject-blind administration of lasmiditan/placebo conducted in healthy subjects.

Subjects will be admitted to the CRU on Day -1 and are expected to remain a resident until all assessments are completed on Day 16; however, subjects may be allowed to leave the CRU at the discretion of the investigator.

Study governance considerations are described in detail in [Appendix 3](#).

Lasmiditan and topiramate doses will be administered at the CRU. Subjects will be randomly assigned in a 2:1 ratio to receive lasmiditan or placebo on both lasmiditan dosing days (Days 1 and 14). A single oral dose of study drug (200-mg lasmiditan or placebo) will be administered in the morning on Day 1. After lasmiditan wash-out, topiramate will be titrated up to 100 mg on Days 3 to 13. On Day 14, 1 oral dose of lasmiditan 200 mg or placebo will be co-administered with the final topiramate dose (50 mg) in the morning.

Blood sampling for PK assessment will be conducted predose and at time points up to 48 hours postdose on Days 1 and 14 for the measurement of plasma concentrations of lasmiditan and its metabolites. Blood samples will also be collected predose and up to 12 hours postdose on Days 13 and 14 for the measurement of plasma concentrations of topiramate.

A follow-up visit will take place at least 10 days following co-administration of lasmiditan and topiramate (Day 14).

9.5. Pharmacokinetics

At the visits and times specified in the Schedule of Activities, venous blood samples of approximately 3 mL each will be collected to determine the plasma concentrations of lasmiditan and its metabolites. Similarly, at times specified in the Schedule of Activities, 2 mL of venous blood samples will be collected to determine the plasma concentrations of topiramate. A maximum of 3 samples may be collected at additional time points during the study if warranted and agreed upon between both the investigator and sponsor. Instructions for the collection and handling of blood samples will be provided by the sponsor. The actual date and time (24-hour clock time) of each sampling will be recorded.

9.5.1. Bioanalysis

Samples will be analyzed at a laboratory approved by the sponsor and stored at a facility designated by the sponsor.

Concentrations of lasmiditan and its metabolites will be assayed using a validated liquid chromatography tandem-mass spectrometry (LC-MS/MS) method. Analyses of samples collected from subjects who received placebo are not planned.

Concentrations of topiramate will be assayed using a validated LC-MS/MS method.

Bioanalytical samples collected to measure IP concentrations will be retained for a maximum of 2 years following last subject visit for the study. During this time, samples remaining after the bioanalyses may be used for exploratory analyses.

10.3.2.1. Pharmacokinetic Parameter Estimation

Pharmacokinetic parameter estimates for lasmiditan and its metabolites, and topiramate will be calculated using standard noncompartmental methods of analysis and summarized using descriptive statistics.

The primary parameters for analysis will be C_{max} , t_{max} , AUC(0-tlast) and AUC from zero to infinity for lasmiditan and its metabolites on Days 1 and 14, and C_{max} , t_{max} , and AUC during 1 dosing interval for topiramate on Days 13 and 14. Other noncompartmental parameters, such as half-life, apparent clearance, and apparent volume of distribution may be reported.

10.3.2.2. Pharmacokinetic Statistical Inference

Pharmacokinetic parameters will be evaluated to determine the impact of topiramate co-administration on the PK of a single dose of lasmiditan and its metabolites. Log-transformed C_{max} and AUC parameters will be evaluated in a linear mixed-effects model with fixed effects for treatment (lasmiditan co-administered with topiramate [Day 14; test treatment] versus lasmiditan alone [Day 1; reference treatment]), and a random effect for subject. The treatment differences will be back-transformed to present the ratios of geometric means and the corresponding 90% confidence interval (CI).

Appendix 5. Blood Sampling Summary

This table summarizes the approximate number of venipunctures and blood volumes for all blood sampling (screening, safety laboratories, and bioanalytical assays) during the study.

Protocol H8H-MC-LAHT Sampling Summary

Purpose	Blood Volume per Sample (mL)	Number of Blood Samples	Total Volume (mL)
Screening tests ^a	45	1	45
Clinical laboratory tests ^a	12.5	5	62.5
Lasmiditan and metabolite pharmacokinetics ^b	3	27	81
Topiramate pharmacokinetics ^b	2	20	40
Pharmacogenetics	10	1	10
Total			238.5
Total for clinical purposes rounded up to the nearest 10 mL			240

^a Additional samples may be drawn if needed for safety purposes.

^b Includes a potential 3 additional samples.

Leo Document ID = 9147c1ba-6644-46bd-a6c6-a9340b641595

Approver: PPD

Approval Date & Time: 19-Oct-2017 17:11:26 GMT

Signature meaning: Approved

Approver: PPD

Approval Date & Time: 20-Oct-2017 08:36:56 GMT

Signature meaning: Approved

2. ABBREVIATIONS

Abbreviations pertain to the Statistical Analysis Plan (SAP) only (not the tables, figures and listings [TFLs]).

AE	Adverse event
ALP	Alkaline phosphatase
ALT	Alanine aminotransferase
AUC	Area under the concentration versus time curve
AUC _τ	Area under the concentration versus time curve during one dosing interval
AUC(0-t _{last})	Area under the concentration versus time curve from time zero to time t, where t is the last time point with a measurable concentration
AUC(0-∞)	Area under the concentration versus time curve from time zero to infinity
%AUC(t _{last} -∞)	Percentage of AUC(0-∞) extrapolated
bid	Twice daily
BQL	Below the lower limit of quantification
CI	Confidence interval
C _{max}	Maximum observed drug concentration
CL/F	Apparent total body clearance of drug calculated after extra-vascular administration
CRF	Case Report Form
CRU	Clinical research unit
CSR	Clinical Study Report
C-SSRS	Columbia Suicide Severity Rating Scale
CRU	Clinical Research Unit
CV	Coefficient of variation
EC	Early Clinical
ECG	Electrocardiogram
e.g.	For example (Latin: exempli gratia)
ICH	International Council on Harmonisation
LLOQ	Lower limit of quantification
MedDRA	Medical Dictionary for Regulatory Activities
MR	Metabolic ratio
MRE	Magnetic resonance elastography

qd	Once daily
QTc	QT correction; QT interval corrected for heart rate
QTcB	QTc calculated using the Bazett correction
QTcF	QTc calculated using the Fridericia correction
PK	Pharmacokinetic
SAP	Statistical Analysis Plan
SD	Standard deviation
TBL	Total bilirubin
TFLs	Tables, Figures, and Listings
$t_{1/2}$	Half-life associated with the terminal rate constant (λ_z) in non-compartmental analysis
t_{max}	Time of maximum observed drug concentration
ULN	Upper limit of normal
V_{ss}/F	Apparent volume of distribution at steady state after extra-vascular administration
V_z/F	Apparent volume of distribution during the terminal phase after extra-vascular administration
WHO	World Health Organization

3. INTRODUCTION

This SAP has been developed after review of the Clinical Study Protocol (final version dated 03 August 2017 and Protocol Amendment (c) (final version dated 20 October 2017).

This SAP describes the planned analysis of the safety, tolerability and pharmacokinetic (PK) data from this study. A detailed description of the planned TFLs to be presented in the clinical study report (CSR) is provided in the accompanying TFL shell document.

The intent of this document is to provide guidance for the statistical and PK analyses of data. In general, the analyses are based on information from the protocol, unless they have been modified by agreement between Eli Lilly and Company and Covance Early Clinical (EC) Biometrics. A limited amount of information concerning this study (e.g., objectives, study design) is given to help the reader's interpretation. This SAP must be signed off prior to first subject administration for this study. When the SAP and TFL shells are agreed upon and finalized, they will serve as the template for this study's CSR.

This SAP supersedes the statistical considerations identified in the protocol; where considerations are substantially different, they will be so identified. If additional analyses are required to supplement the planned analyses described in this SAP, they may be performed and will be identified in the CSR. Any substantial deviations from this SAP will be agreed upon between Eli Lilly and Company and Covance EC Biometrics and identified in the CSR. Any minor deviations from the TFLs may not be documented in the CSR.

This SAP is written with consideration of the recommendations outlined in the International Council on Harmonisation (ICH) E9 Guideline entitled Guidance for Industry: Statistical Principles for Clinical Trials¹ and the ICH E3 Guideline entitled Guidance for Industry: Structure and Content of Clinical Study Reports².

4. STUDY OBJECTIVES

4.1 Primary Objective

- To evaluate the safety and tolerability of a single dose of lasmiditan in combination with topiramate in healthy subjects.

4.2 Secondary Objectives

- To evaluate the PK of lasmiditan alone and in combination with topiramate in healthy subjects.
- To evaluate the PK of topiramate alone and in combination with lasmiditan.

4.3 Exploratory Objectives

- To evaluate the PK of lasmiditan metabolites alone and in combination with topiramate in healthy subjects.

5. STUDY DESIGN

This is a Phase 1, parallel, placebo-controlled, fixed-sequence study with open-label administration of topiramate and investigator- and subject-blind administration of lasmiditan/placebo conducted in healthy subjects.

Subjects will be admitted to the Clinical Research Unit (CRU) on Day -1 and are expected to remain a resident until all assessments are completed on Day 16; however, subjects may be allowed to leave the CRU at the discretion of the investigator.

[figure not shown]
Study governance considerations are described in detail in Appendix 3 of the protocol.

Lasmiditan and topiramate doses will be administered at the CRU. Subjects will be randomly assigned in a 2:1 ratio to receive lasmiditan or placebo on both lasmiditan dosing days (Days 1 and 14). A single oral dose of study drug (200 mg lasmiditan or placebo) will be administered in the morning on Day 1. After lasmiditan wash-out, topiramate will be titrated up to 100 mg on Days 3 to 13. On Day 14, 1 oral dose of lasmiditan 200 mg or placebo will be co-administered with the final topiramate dose (50 mg) in the morning.

Blood sampling for PK assessment will be conducted predose and at time points up to 48 hours postdose on Days 1 and 14 for the measurement of plasma concentrations of lasmiditan and its metabolites. Blood samples will also be collected predose and up to 12 hours postdose on Days 13 and 14 for the measurement of plasma concentrations of topiramate.

A follow-up visit will take place at least 10 days following co-administration of lasmiditan and topiramate (Day 14).

Figure 1 illustrates the study design.

Abbreviations: LY = lasmiditan (200 mg); n = number of subjects in each group; P = placebo.
Symbols: "25" inside a circle = one 25 mg tablet of topiramate; gray pentagon = lasmiditan dose or placebo

Figure 1. Illustration of study design

6. TREATMENTS

The following is a list of the study treatment abbreviations that will be used in the TFLs.

Study Treatment Name	Treatment order in TFL
Placebo	1
200 mg lasmiditan	2
25 mg topiramate QD	3
25 mg topiramate BID	4
50 mg topiramate BID	5
50 mg topiramate + placebo	6
50 mg topiramate + 200 mg lasmiditan	7

D = Day; QD = once daily; BID = twice daily

The following treatment sequences may be displayed across some outputs.

Sequence	Treatment Sequence Description
1	Placebo / 25 mg topiramate QD / 25 mg topiramate BID / 25 mg topiramate BID / 50 mg topiramate BID / 50 mg topiramate + placebo
2	200 mg lasmiditan / 25 mg topiramate QD / 25 mg topiramate BID / 25 mg topiramate BID / 50 mg topiramate BID / 50 mg topiramate + 200 mg lasmiditan

7. SAMPLE SIZE JUSTIFICATION

Approximately 30 subjects will be enrolled, so that at least 21 subjects complete the study. Subjects will be randomized in a 2:1 ratio of lasmiditan 200 mg : placebo. The sample size is customary for Phase 1 studies evaluating safety and tolerability, and is not powered on the basis of statistical hypothesis testing.

Subjects who are randomized but who do not complete Day 14 treatment may be replaced to ensure that enough subjects complete the study.

8. DEFINITION OF ANALYSIS POPULATIONS

The “Safety” population will consist of all enrolled subjects, whether or not they completed all protocol requirements.

The “PK” population will consist of all subjects who received at least one dose of lasmiditan or topiramate and have evaluable PK data. Subjects may be excluded from the PK summary statistics and statistical analysis if a subject has an adverse event (AE) of vomiting that occurs at or before 2 times median time of maximum observed concentration (t_{max}).

All protocol deviations that occur during the study will be considered for their severity/impact and will be taken into consideration when subjects are assigned to analysis populations.

9. STATISTICAL METHODOLOGY

9.1 General

Data listings will be provided for all data that is databased. Summary statistics and statistical analysis will only be presented for data where detailed in this SAP. For continuous data, summary statistics will include the arithmetic mean, arithmetic standard deviation (SD), median, min, max and N; for log-normal data (e.g. the PK parameters: area under the concentration versus time curve [AUCs] and maximum observed drug concentration [C_{max}]) the geometric mean and geometric coefficient of variation (CV%) will also be presented. For categorical data, frequency count and percentages will be presented. Data listings will be provided for all subjects up to the point of withdrawal, with any subjects excluded from the relevant population highlighted. Summary statistics and statistical analyses will generally only be performed for subjects included in the relevant analysis population. For the calculation of summary statistics and statistical analysis, unrounded data will be used.

Mean change from baseline is the mean of all individual subjects' change from baseline values. Each individual change from baseline will be calculated by subtracting the individual subject's baseline value from the value at the timepoint. The individual subject's change from baseline values will be used to calculate the mean change from baseline using a SAS procedure such as Proc Univariate.

Data analysis will be performed using SAS® Version 9.3 or greater.

9.2 Demographics and Subject Disposition

Subject disposition will be listed. The demographic variables age, sex, race, ethnicity, country of enrolment, site ID, body weight, height and body mass index will be summarized and listed.

9.3 Pharmacokinetic Assessment

9.3.1 Pharmacokinetic Analysis

PK parameter estimates will be determined using non-compartmental procedures in validated software program (Phoenix WinNonlin Version 6.4 or later).

Plasma concentrations of lasmiditan (LY573144) and its metabolites will be used to determine the following PK parameters, when possible:

Parameter	Units	Definition
C_{\max}	ng/mL	maximum observed drug concentration
t_{\max}	h	time of maximum observed drug concentration
$AUC(0-\infty)$	ng.h/mL	area under the concentration versus time curve from time zero to infinity
$AUC(0-t_{\text{last}})$	ng.h/mL	area under the concentration versus time curve from time zero to time t , where t is the last time point with a measurable concentration
% $AUC(t_{\text{last}}-\infty)$	%	percentage of $AUC(0-\infty)$ extrapolated
$t_{\frac{1}{2}}$	h	half-life associated with the terminal rate constant (λ_z) in non-compartmental analysis
CL/F	L/h	apparent total body clearance of drug calculated after extra-vascular administration (LY573144 only)
V_z/F	L	apparent volume of distribution during the terminal phase after extra-vascular administration (LY573144 only)
V_{ss}/F	L	apparent volume of distribution at steady state after extra-vascular administration (LY573144 only)
MR		Metabolic ratio ^a

^a no molar correction will be applied since the metabolites are very similar in molecular weight and within 5% of the molecular weight for lasmiditan.

Plasma concentrations of topiramate will be used to determine the following PK parameters, when possible:

Parameter	Units	Definition
C_{\max}	ng/mL	maximum observed drug concentration
t_{\max}	h	time of maximum observed drug concentration
AUC_{τ}	ng.h/mL	area under the concentration versus time curve during one dosing interval
CL/F	L/h	apparent total body clearance of drug calculated after extra-vascular administration

Additional PK parameters may be calculated, as appropriate. The software and version used for the final analyses will be specified in the CSR. Any exceptions or special handling of data will be clearly documented within the final study report.

Formatting of tables, figures and abbreviations will follow the Eli Lilly Global PK/PD/TS Tool: NON-COMPARTMENTAL PHARMACOKINETIC STYLE GUIDE. The version of the tool effective at the time of PK analysis will be followed.

General PK Parameter Rules

- Actual sampling times will be used in the final analyses of individual PK parameters, except for non-bolus pre-dose sampling times which will be set to zero. For non-bolus, multiple dose profiles, the pre-dose time will be set to zero unless a time deviation falls outside of the protocol blood collection time window which is considered to impact PK parameter derivation.
- C_{\max} and t_{\max} will be reported from observed values. If C_{\max} occurs at more than one time point, t_{\max} will be assigned to the first occurrence of C_{\max} .
- AUC parameters will be calculated using a combination of the linear and logarithmic trapezoidal methods (linear-log trapezoidal rule). The linear trapezoidal method will be applied up to t_{\max} and then the logarithmic trapezoidal method will be used after t_{\max} . The minimum requirement for the calculation of AUC will be the inclusion of at least three consecutive plasma concentrations above the lower limit of quantification (LLOQ), with at least one of these concentrations following C_{\max} . AUC(0-∞) values where the percentage of the total area extrapolated is more than 20% will be flagged. Any AUC(0-∞) value excluded from summary statistics will be noted in the footnote of the summary table.
- Half-life ($t_{1/2}$) will be calculated, when appropriate, based on the apparent terminal log-linear portion of the concentration-time curve. The start of the terminal elimination phase for each subject will be defined by visual inspection and generally will be the first point at which there is no systematic deviation from the log-linear decline in plasma concentrations. Half-life will only be calculated when a reliable estimate for this parameter can be obtained comprising of at least 3 data points. If $t_{1/2}$ is estimated over a

time window of less than 2 half-lives, the values will be flagged in the data listings. Any $t_{1/2}$ value excluded from summary statistics will be documented in the footnote of the summary table.

- A uniform weighting scheme will be used in the regression analysis of the terminal log-linear portion of the concentration-time curve.
- The parameters based on predicted C_{last} will be reported.

Individual PK Parameter Rules

- Only quantifiable concentrations will be used to calculate PK parameters with the exception of special handling of certain concentrations reported below the lower limit of quantitation (BQL). Plasma concentrations reported as BQL will be set to a value of zero when all of the following conditions are met:
 - The compound is non-endogenous.
 - The samples are from the initial dose period for a subject or from a subsequent dose period following a suitable wash-out period.
 - The time points occur before the first quantifiable concentration.
- All other BQL concentrations that do not meet the above criteria will be set to missing.
- Also, where two or more consecutive concentrations are BQL towards the end of a profile, the profile will be deemed to have terminated and therefore any further quantifiable concentrations will be set to missing for the calculation of the PK parameters unless it is considered to be a true characteristic of the profile of the drug.

Individual Concentration vs. Time Profiles

- Individual concentrations will be plotted utilizing actual sampling times.
- The terminal point selections will be indicated on a semi-logarithmic plot.

Average Concentration vs. Time Profiles

- The average concentration profiles will be graphed using scheduled (nominal) sampling times.
- The average concentration profiles will be graphed using arithmetic average concentrations.
- The pre-dose average concentration for single-dose data from non-endogenous compounds will be set to zero. Otherwise, only quantifiable concentrations will be used to calculate average concentrations.

- Concentrations at a sampling time exceeding the sampling time window specified in the protocol, or $\pm 10\%$, will be excluded from the average concentration profiles.
- Concentrations excluded from the mean calculation will be documented in the final study report.
- A concentration average will be plotted for a given sampling time only if 2/3 of the individual data at the time point have quantifiable measurements that are within the sampling time window specified in the protocol or $\pm X\%$. An average concentration estimated with less than 2/3 but more than 3 data points may be displayed on the mean concentration plot if determined to be appropriate and will be documented within the final study report.

Treatment of Outliers during Pharmacokinetic Analysis

Application of this procedure to all PK analyses is not a requirement. Rather, this procedure provides justification for exclusion of data when scientifically appropriate. This procedure describes the methodology for identifying an individual value as an outlier for potential exclusion, but does not require that the value be excluded from analysis. The following methodology will not be used to exclude complete profiles from analysis.

Data within an Individual Profile

A value within an individual profile may be excluded from analysis if any of the following criteria are met:

- For PK profiles during multiple dosing, the concentration of the pre-dose sample exceeds all measured concentrations for that individual in the subsequent post-dose samples.
- For PK profiles during single dosing of non-endogenous compounds, the concentration in a pre-dose sample is quantifiable.
- For any questionable datum that does not satisfy the above criteria, the profile will be evaluated and results reported with and without the suspected datum.

Data between Individual Profiles

1. If $n < 6$, then the dataset is too small to conduct a reliable range test. Data will be analyzed with and without the atypical value, and both sets of results will be reported.
2. If $n \geq 6$, then an objective outlier test will be used to compare the atypical value to other values included in that calculation:
 - a. Transform all values in the calculation to the logarithmic domain.
 - b. Find the most extreme value from the arithmetic mean of the log transformed values and exclude that value from the dataset.

- c. Calculate the lower and upper bounds of the range defined by the arithmetic mean $\pm 3*SD$ of the remaining log-transformed values.
- d. If the extreme value is within the range of arithmetic mean $\pm 3*SD$, then it is not an outlier and will be retained in the dataset.
- e. If the extreme value is outside the range of arithmetic mean $\pm 3*SD$, then it is an outlier and will be excluded from analysis.

If the remaining dataset contains another atypical datum suspected to be an outlier and $n \geq 6$ following the exclusion, then repeat step 2 above. This evaluation may be repeated as many times as necessary, excluding only one suspected outlier in each iteration, until all data remaining in the dataset fall within the range of arithmetic mean $\pm 3*SD$ of the log-transformed values.

Reporting of Excluded Values

Individual values excluded as outliers will be documented in the final report. Approval of the final report will connote approval of the exclusion.

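### SAP 9.3.1 leaves open whether a flagged PK outlier may or must be excluded, and with six or more values it does not require the result with the value kept in

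*SAP*

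**What the plan says.** The outlier procedure is in SAP 9.3.1, under the heading on treatment of outliers. Its preamble makes it optional: "Application of this procedure to all PK analyses is not a requirement". It describes a way to identify a value for potential exclusion that "does not require that the value be excluded from analysis", and it adds a limit: "The following methodology will not be used to exclude complete profiles from analysis".

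For comparisons between profiles there are two branches.

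- **n<6:** "Data will be analyzed with and without the atypical value, and both sets of results will be reported".
- **n≥6:** "an objective outlier test will be used to compare the atypical value to other values included in that calculation". The most extreme log value is set aside, and the mean and SD are taken from the rest. If the value lies outside mean ± 3 SD, step 2e applies: "then it is an outlier and will be excluded from analysis". The step may be repeated while at least six values remain.

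Within a single profile, a questionable datum that meets neither listed criterion also gets both results: "the profile will be evaluated and results reported with and without the suspected datum".

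On reporting, excluded values are documented in the final report, and "Approval of the final report will connote approval of the exclusion". SAP 9.3.2 then specifies the mixed model for the Day 14 versus Day 1 ratios and 90% CIs. It permits additional analyses but names no sensitivity analysis for excluded values.

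**The concern.** Two things do not fit together. The preamble says that identifying a value does not compel its exclusion, while step 2e compels it. And the SAP asks for both results in the n<6 branch and for certain within-profile data, but not in the branch where an interaction ratio would normally be estimated.

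Two analysts who both follow the SAP could therefore report different geometric mean ratios and 90% CIs from the same data, and the report need not print the second pair. An interaction study is also where a single subject with a large exposure change on the combination is of interest. A rule that may drop that value should leave the result with it in view. The PK ratios matter because SAP 9.4.10 plans no inferential analysis of safety.

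**Working it through.** **1. Which branch applies.** SAP 7 gives about 30 enrolled, at least 21 completing, and 2:1 allocation. The lasmiditan arm is 30 × 2/3 = 20 enrolled, or 21 × 2/3 = 14 completers if completers also split 2:1. If all 9 losses fell in that arm, 20 − 9 = 11 would remain. All of these exceed six. The SAP gives no power calculation or error rate for the test, so there is no stated figure to reproduce.

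**2. How often the test fires on clean data.** Assume normal log values and a test run every time. For one value compared with the other n − 1, the difference divided by SD_rest × √(n/(n−1)) follows t with n − 2 df. The chance per value is therefore 2·P(t_{n−2} > 3/√(n/(n−1))). At these sizes, n times that closely approximates the chance of at least one exclusion.

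| n | 3/√(n/(n−1)) | per value | × n | simulated |
|---|---|---|---|---|
| 11 | 2.860 | 1.88% | 20.6% | 20.5% |
| 14 | 2.891 | 1.36% | 19.0% | 18.7–19.1% |
| 20 | 2.924 | 0.91% | 18.1% | 17.9–18.1% |

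If both days are pooled as one calculation, the simulated rate is 11–18%. Tested per day, an exclusion on Day 1 or Day 14 occurs in 27–34% of comparisons for one parameter.

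**3. Effect on the ratio in clean data.** Total CVs of 45% (AUC) and 61% (Cmax) are the upper intersubject values in Protocol 3.2. Within-subject CVs are not in the documents. They are assumed at 15–30% for AUC and 20–40% for Cmax. There is no treatment effect, the rule is applied per day, and the SAP model is fitted before and after exclusion. Among comparisons with an exclusion:

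| | n=14 | n=20 |
|---|---|---|
| Median absolute change, AUC ratio | 2.2–6.3% | 1.6–4.5% |
| Median absolute change, Cmax ratio | 2.9–8.2% | 2.2–6.0% |
| 95th percentile, AUC ratio | 5.2–13.4% | 3.6–10.1% |
| 95th percentile, Cmax ratio | 6.9–18.3% | 4.9–12.6% |

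The mean change factor is 0.996–1.004, so there is no average bias. The 90% CI width on the log scale changes by a median factor of 1.00–1.07 (5th to 95th percentile 0.75–1.21) and narrows in 24–49% of these comparisons.

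**4. A genuine individual interaction.** Give one subject a true 3-fold rise in Day 14 AUC, with between-subject CV 45% and assumed within-subject CV 20–30%. Step 2e removes that value in 23–32% of simulated datasets (n=14 or 20, including a repeat run). For a 4-fold rise the figure is 39–51%.

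The size of the shift follows from simple arithmetic. On the log scale a CV of 45% is an SD of √ln(1 + 0.45²) = 0.429. Suppose one subject's log ratio is 3.2 × 0.429 = 1.374 and all others centre on zero. The mean log ratio moves by 1.374/14 = 0.098 at n=14 and 1.374/20 = 0.069 at n=20. With within-subject CV 20% and a simple paired analysis that drops the subject's pair:

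- n=14: 1.10 (90% CI 0.89–1.37) with the value, 1.00 (0.87–1.15) without.
- n=20: 1.07 (0.91–1.26) with, 1.00 (0.89–1.12) without.

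This shows the size of the change if such a value is dropped. It does not show that the test would always drop it.

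**The case against.** **The wording has a natural reading.** The preamble sets the status of everything beneath it: running the test is optional, and step 2e binds once it is run. This is available, but the SAP does not say it, and the preamble's disclaimer attaches to a value the procedure has already identified. Even so read, the choice to run the test stays open after data are seen, because atypical has no criterion.

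**The link to the mixed model is an inference.** The procedure is in 9.3.1, the model is in 9.3.2, and neither refers to the other. SAP 8 names both summary statistics and statistical analysis when it means both; step 2e says only analysis. This stands, and the figures for the ratio depend on it.

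**The 18–19% is not a forecast.** A reader might infer that nearly one in five lasmiditan analyses will lose a valid value. The documents do not support that, since the test is run only on a value judged atypical.

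**Computing the SD without the suspect value is not itself an error.** A limit based on a known SD would flag 1 − (1 − 0.0027)^n = 3.7% (n=14) or 5.3% (n=20) of clean datasets, but no known SD exists here. With the suspect value kept in, the largest possible standardised deviation at n=14 is 13/√14 = 3.47, and only about 0.1% (n=14) or 1.0% (n=20) of clean datasets would be flagged. The SAP states the method openly.

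**Exclusions are not hidden.** Special handling and excluded values must be documented (9.3.1), excluded AUC(0-∞) values are footnoted, and data are listed (9.1). This answers any suggestion of concealment. It does not supply the ratio with the value retained.

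**Large interactions may survive.** At the upper CVs, a subject near the geometric mean needs about a 3.6-fold AUC shift (exp(3 × 0.429)) or a 5.4-fold Cmax shift (exp(3 × 0.562)) to pass 3 SD. The ban on excluding complete profiles may also protect some cases, though the SAP does not say whether dropping a subject's derived AUC counts as that. An interaction shared by all subjects is unaffected.

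**Conclusion.** The inconsistency and the reporting gap at n≥6 are both in the text and should be repaired. The gap reaches the lasmiditan ratios only if the procedure feeds the 9.3.2 model, which is likely but unstated. If a value is excluded, the ratio typically moves by about 2–8%, more in the tail, under assumed within-subject CVs. A real individual effect could be removed unless the profile ban prevents it.

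Three stronger readings go too far. The procedure does not bias the ratio on average in clean data. The SAP does not say that exclusions will be chosen after the ratios are seen; it is silent on timing, and approval through the final report leaves that possible. And reporting a main result without outliers is not wrong in itself.

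Severity is minor to moderate. PK is a secondary objective, the primary safety evaluation is untouched, and the SAP sets no decision bound for the ratios.

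**What to change.** - Reword step 2e so that a value outside the range is flagged for possible exclusion, in line with the preamble.
- For n≥6, whenever a value is excluded, report the geometric mean ratio and 90% CI with and without it, as the n<6 branch already requires.
- State whether the procedure determines the inputs to the 9.3.2 model.
- Require the decision and its reason to be recorded before treatment ratios are produced.
- Pre-specify which result is the main one. All evaluable values is a reasonable default, but this is a choice and not a correction of an error. Its drawback is that a truly erroneous value stays in the main result and may widen its 90% CI, with the other result alongside.

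The cost is a few sentences of SAP text, one extra model run when a value is flagged, and two results to present in that case.
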